## **11.5 Efficacy Endpoints**

The two co-primary efficacy endpoints are (1) the baseline-adjusted area under the serial FEV1-time curve calculated from time zero to 12 hours (AUC0-12h) on Day 1 of treatment (Visit 2), and (2) the baseline-adjusted pre-dose FEV1 measured in the morning of Day  $29 \pm 2$  (Visit 3), after the last dose in the prior evening.

## **11.6 Primary Endpoint Analyses**

The Baseline  $FEV_1$  will be subtracted from post-dose  $FEV_1$  values to obtain the baseline-corrected values. Baseline-adjusted area under the serial  $FEV_1$ -time curve from time zero to 12 hours (AUC0-12h) will be calculated by the linear trapezoidal method.. The statistical analyses will involve Analysis of Covariance (ANCOVA) with terms for **as fixed effects and using as a covariate in the model**.

A Randomized, Multiple-Dose, Blinded, Placebo-Controlled, Parallel-Design, Multiple-Center, Clinical Study to Evaluate the Therapeutic Equivalence of Fluticasone Propionate and Salmeterol Inhalation Powder, 100 mcg/50 mcg (Supplied by Teva Pharmaceuticals Ireland) to ADVAIR DISKUS® 100/50 (fluticasone propionate/salmeterol) Inhalation Powder, (GlaxoSmithKline) in Subjects With Asthma

## Therapeutic Equivalence

Therapeutic equivalence will be evaluated for the primary endpoint in each PP population. Under the assumptions of normally distributed data, the adjusted 90% confidence interval will be calculated for the Test/Reference ratio of the mean baseline-adjusted AUC0-12h on Day 1 **Control** and for the Test/Reference ratio of the mean baseline-adjusted morning pre-dose FEV1 on Day 29  $\pm$  2 **Control** using an iterative procedure similar to Fieller's method. The mean baseline value for use in the iterative procedure will be determined from the Baseline FEV1 of all subjects receiving active treatment in the PP population, without regard to the treatment received. If the adjusted 90% confidence intervals for the least-squares mean Test/Reference ratios are within 80.00-125.00% for both co-primary endpoints, then therapeutic equivalence of the Test to Reference product will be considered to have been demonstrated.

## Superiority to Placebo

The superiority of the Test and Reference products over Placebo is concluded if the values for mean baseline-adjusted AUC0-12h and the mean baseline-adjusted morning pre-dose FEV1 on Day  $29 \pm 2$  for the active treatments are statistically superior to those respective values of the Placebo at the 5% significance level (p < 0.05, two-sided). The superiority of Test and Reference treatments over the Placebo will be evaluated in the same ANCOVA model for Test vs. Placebo and Reference vs. Placebo.

# 11.7 Safety Analysis

All study subjects who were randomized and used the study product on at least one occasion will be included in the comparative safety analysis. Adverse events will be classified using standard Medical Dictionary for Regulatory Activities (MedDRA) terminology Version 21.1 or higher and presented by treatment group. Summary tables listing the type, date of onset, date of resolution, incidence, severity, outcome, action taken, and Investigator's opinion of relationship to the study product will be presented by treatment group for AEs reported after randomization.

Signs and symptoms of asthma will not be considered AEs, unless in the Investigator's opinion, they have increased in frequency and/or severity to such an extent that the Investigator/subject considers that it is in the subject's best interest to be dropped from continued participation in the study and given alternative therapy for their condition.

Concomitant medication used during the study will be tabulated by treatment by subject.

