	within 80.00-125.00% for both co-primary endpoints, then therapeutic equivalence of the Test to Reference product will be considered to have been demonstrated. Superiority to Placebo The superiority of the Test and Reference products over Placebo is concluded if the values for mean baseline-adjusted AUC 0-12h and mean baseline-adjusted morning pre-dose FEV 1 on Day 29 $\pm$ 2 for the active treatments are statistically superior to those respective values of the Placebo at the 5% significance level ( $p < 0.05$ , two-sided). The superiority of Test and Reference treatments over the Placebo will be evaluated in the same ANCOVA model for Test vs. Placebo and Reference vs. Placebo.
Safety Analysis	There will be two Safety populations: All study subjects who were randomized and used the study product on at least one occasion will be included in the comparative safety analysis. Adverse events (AEs) will be classified using standard Medical Dictionary for Regulatory Activities (MedDRA) terminology Version 21.1 or higher and presented by treatment group. Summary tables listing the type, date of onset, date of resolution, incidence, severity, outcome, action taken, and Investigator's opinion of relationship to the study product will be presented by treatment group for AEs reported after randomization. Signs and symptoms of asthma will not be considered AEs, unless in the Investigator's opinion, they have increased in frequency and/or severity to such an extent that the Investigator/subject considers that it is in the subject's best interest to be dropped from continued participation in the study and given alternative therapy for their condition. Concomitant medication used during the study will be tabulated by treatment by subject.
Sample Size Determination	

A Randomized, Multiple-Dose, Blinded, Placebo-Controlled, Parallel-Design, Multiple-Center, Clinical Study to Evaluate the Therapeutic Equivalence of Fluticasone Propionate and Salmeterol Inhalation Powder, 100 mcg/50 mcg (Supplied by Teva Pharmaceuticals Ireland) to ADVAIR DISKUS® 100/50 (fluticasone propionate/salmeterol) Inhalation Powder, (GlaxoSmithKline) in Subjects With Asthma

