#### **10.2.6 Exacerbation of Asthma**

The definition of a clinically significant asthma exacerbation for this clinical trial is based on the official statement from ATS/ERS Task Force on Asthma Control and Exacerbations.

An asthma exacerbation will include at least one of the following:

Asthma exacerbations meeting the pre-defined criteria above must be recorded as AEs. If they meet the definition of an SAE, they should be recorded as such. Any subject who reports the occurrence of an asthma exacerbation meeting the definition above during the Run-in period will be excluded from randomization.

Subjects may also be withdrawn from the study in case of clinically significant worsening of the condition and/or at PI discretion. Clinically meaningful worsening of asthma may be indicated by a significant decrease of  $FEV_1$  and/or PEF at scheduled or unscheduled study visits or during study monitoring; excessive use of rescue medication (i.e.,

; emergency

hospitalization or emergency medical attention related to asthma aggravation/exacerbation; necessary use of additional, excluded medication for the control of asthma exacerbation or its further prevention.

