#### 10.5.10 Adverse Events

At the end of Visit 1, subjects will be questioned about any AEs that occurred during the visit. At Visits 2 and 3subjects will be questioned regarding any changes in their medical status since their previous visit. Any significant changes observed after ICF/assent signing will be reported as AEs.

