## **10.6.1 Adverse Event Definition**

An AE is any untoward medical occurrence in a subject, regardless of whether it has a causal relationship with this treatment.

In this study, any AE occurring after the subject has signed the ICF/assent until the end of followup period should be recorded and reported as an AE.

An AE can, therefore, be any unfavorable and unintended physical sign, symptom, or laboratory parameter that develops or worsens in severity during the course of this study, or significant worsening of the disease under study or of any concurrent disease, whether or not considered related to the study product. A new condition or the worsening of a pre-existing condition will be considered an AE. Stable chronic conditions (such as arthritis) that are present before study entry and do not worsen during this study will not be considered AEs.

Accordingly, an AE can include any of the following:

- intercurrent illnesses
- physical injuries
- events possibly related to concomitant medication

A Randomized, Multiple-Dose, Blinded, Placebo-Controlled, Parallel-Design, Multiple-Center, Clinical Study to Evaluate the Therapeutic Equivalence of Fluticasone Propionate and Salmeterol Inhalation Powder, 100 mcg/50 mcg (Supplied by Teva Pharmaceuticals Ireland) to ADVAIR DISKUS® 100/50 (fluticasone propionate/salmeterol) Inhalation Powder, (GlaxoSmithKline) in Subjects With Asthma

- significant worsening (change in nature, severity, or frequency) of the disease under study or other pre-existing conditions drug interactions
- events occurring during diagnostic procedures or during any washout phase of this study
- laboratory or diagnostic test abnormalities that result in the withdrawal of the subject from the study, are associated with clinical signs and symptoms or a serious adverse event (SAE), or require medical treatment or further diagnostic work up, or are considered by the Investigator to be clinically significant
- A treatment-emergent AE is any AE that occurs after initiation of study product, or any event already present that worsens in either intensity or frequency following exposure to study product.

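### Protocol 11.7 and the synopsis make the AE status of increased asthma symptoms depend on a judgement to drop the subject; the AE definition in 10.6.1 sets no such condition

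*Protocol*

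**What the plan says.** Protocol 11.7 states: "Signs and symptoms of asthma will not be considered AEs, unless in the Investigator's opinion, they have increased in frequency and/or severity". It then says how large the increase must be: large enough that the Investigator or the subject "considers that it is in the subject's best interest to be dropped from continued participation in the study" and be given other therapy. The Safety Analysis row of the synopsis carries the same rule, opening "Signs and symptoms of asthma will not be considered AEs".

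Protocol 10.6.1 defines AEs differently. It says "A new condition or the worsening of a pre-existing condition will be considered an AE". It lists "significant worsening (change in nature, severity, or frequency) of the disease under study" among the things an AE can include. It also has its own exclusion for background disease: "Stable chronic conditions (such as arthritis) that are present before study entry and do not worsen during this study will not be considered AEs". None of these statements refers to dropping the subject.

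Two other places bear on the point. Protocol 10.2.6 says "Asthma exacerbations meeting the pre-defined criteria above must be recorded as AEs". Protocol 10.5.10, on questioning at visits, says "Any significant changes observed after ICF/assent signing will be reported as AEs".

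**The concern.** An AE definition should give one answer for one event. Section 11.7 speaks expressly of asthma symptoms that have increased, and still withholds AE status until someone judges that the subject would be better off out of the study. Section 10.6.1 grants AE status on the worsening itself.

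At stake is the completeness of the by-treatment AE tables for the disease under study. Inclusion criterion 9 requires subjects to be able to stop their asthma medications for the run-in and the rest of the study, and one arm receives placebo, so some worsening is foreseeable. A site that followed 11.7 could leave it unrecorded as an AE while a site that followed 10.6.1 recorded it. SAP 8.3.1 codes and tabulates the AEs that were reported; it cannot recover those that were not.

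**Working it through.** No arithmetic applies. The documents give no rate of worsening and no share of worsening subjects who continue. The check is to run the two rules over the possible cases.

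| Case | 11.7 and synopsis | 10.6.1 | Result |
|---|---|---|---|
| A. Asthma symptoms present at entry, not worse | Not an AE | Not an AE (stable chronic condition) | Agree |
| B. Worsening, and dropping the subject is judged best | AE | AE | Agree |
| C. Defined exacerbation, dropping not judged best | Component symptoms not AEs | AE; recording also mandatory under 10.2.6 | Can stand together if 10.2.6 governs the event and 11.7 only its symptoms |
| D. Significant worsening short of a defined exacerbation, dropping not judged best | Not an AE | AE | Opposite answers |
| E. Lesser worsening, dropping not judged best | Not an AE | AE under the plain worsening sentence; not reached by the significant-worsening statements | Opposite answers, and 10.6.1 is unclear in itself |

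**Can D and E occur?** Yes. Protocol 10.2.5 leaves withdrawal for worsening to Investigator judgement, and 10.2.6 says only that subjects may be withdrawn. The protocol therefore allows for subjects who worsen and continue. The test in 11.7 is a view about the subject's best interest and not withdrawal itself, but a subject who continues will usually be one for whom that view was not reached.

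**Does another section settle D and E?**

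- Protocol 10.6.7 exempts manifestations of a disease from being recorded one by one and asks for a diagnosis where possible. That narrows the conflict. It governs how symptoms are grouped, and does not make AE status turn on dropping the subject.
- Protocol 10.5.10 points the same way as 10.6.1, but it is a general instruction that does not mention asthma or say what counts as significant.
- SAP 8.3 to 8.3.1, as visible, contains no asthma exclusion, and Protocol 11.1 gives the SAP precedence over the protocol. The visible analysis therefore applies no exclusion, but what sites record is left open. The list of changes in SAP 8.7 cannot be read in the public text.
- Protocol 10.6.8 promises a Safety Plan that overrides the protocol on collecting and recording AEs. It was not supplied, so it may or may not settle the matter.

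The conflict is thus between 11.7 with the synopsis on one side and 10.6.1 on the other, for cases D and E.

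**The case against.** The best case for the plan has four parts.

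1. **Position.** Section 11.7 sits under statistical methods; recording instructions are in section 10, and 10.6.7 requires every AE in the study period to be recorded. A site would have to prefer an analysis sentence to the AE definition. This makes harm less likely, but 11.7 is worded as a rule on what counts as an AE, and the synopsis repeats it.
2. **Subject matter.** Section 11.7 concerns signs and symptoms, 10.2.6 a defined event. This stands. A reader might infer that 11.7 contradicts 10.2.6 and that exacerbations could be lost. The documents do not support that, because the specific mandatory rule can operate beside a rule on component symptoms, and SAEs have their own reporting duty in 10.6.8. Nor should 10.5.10 be read as a separate contradiction; 11.7 could be taken as saying what is significant for asthma.
3. **Other capture.** Diaries record rescue use and concomitant medication, 11.7 tabulates concomitant medication, and home peak flow is collected for interim safety monitoring. What may be lost is the AE label, not all evidence of worsening. This stands.
4. **Unseen sources.** The Safety Plan may already resolve the point. This stands as a limit on size, but it does not make the protocol consistent.

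A reader might also infer bias against one arm or a threat to the efficacy result. SAP 4 blinds the Investigator and no rates by arm are given, so no direction can be claimed. Equivalence and superiority rest on FEV1 endpoints and use no AE counts.

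**Conclusion.** The inconsistency is real and can be seen without any hidden text: 11.7 and the synopsis conflict directly with 10.6.1 on asthma that worsens in a subject whom nobody judges should be dropped. It is a minor to moderate wording problem in AE recording.

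Its size cannot be estimated. The exacerbation criteria in 10.2.6 are not visible, so the group falling short of them cannot be bounded. The undercount is zero if every site follows section 10 or if the Safety Plan resolves the conflict. It exceeds zero only if some site applies 11.7 literally to a subject who worsens and continues. The conclusion rests on reading 11.7 as written and on withdrawal being discretionary, as 10.2.5 and 10.2.6 say.

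**What to change.** In 11.7 and the synopsis, add one sentence stating that the asthma exclusion covers signs and symptoms that have not worsened, does not limit 10.6.1 or the mandatory recording in 10.2.6, and that AE status does not depend on the judgement to drop the subject.

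In the same edit, reconcile 10.6.1 with itself. It uses both significant worsening and plain worsening, and for the disease under study it should say which applies; otherwise case E stays open. Then confirm that the Safety Plan says the same and that SAP 8.7 does not carry the exclusion into the AE tables. No change to the withdrawal rules is proposed.

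The cost is one sentence in two places, a clarification in 10.6.1 and two document checks, with the IRB review that Protocol 12.2.3 requires for any revision. No new data collection or table is needed. The downside is that AE counts may rise by an unknown amount, more so if plain worsening is the wording kept.

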# **12.0 REGULATORY OBLIGATIONS**

# 12.1 Institutional Review Board

The study protocol, ICF, product label (as applicable) and any specific advertising will be submitted to, and approved by, an IRB before the start of the study. A form must be signed by the chairman or designee of the IRB noting the approvals. This notification of the board's approval along with a

A Randomized, Multiple-Dose, Blinded, Placebo-Controlled, Parallel-Design, Multiple-Center, Clinical Study to Evaluate the Therapeutic Equivalence of Fluticasone Propionate and Salmeterol Inhalation Powder, 100 mcg/50 mcg (Supplied by Teva Pharmaceuticals Ireland) to ADVAIR DISKUS® 100/50 (fluticasone propionate/salmeterol) Inhalation Powder, (GlaxoSmithKline) in Subjects With Asthma

description by profession and gender of the board's composition will be provided to the Sponsor and/or Sponsor Representative.

## **12.2 Study Documentation**

This study will be conducted in compliance with the protocol; Good Clinical Practices and all applicable regulations, including the Federal Food, Drug, and Cosmetics Act, United States (US) applicable Code of Federal Regulations (title 21), parts 50, 56, 312, 320, and any IRB requirements relative to clinical studies; and the Declaration of Helsinki, June 1964, as modified by the 64th World Medical Association General Assembly, October 2013. The Investigator will permit trial-related monitoring, audits, IRB review and regulatory inspections providing direct access to source data/documents.

## 12.2.1 Protocol

The Investigator indicated on FDA Form 1572 will act as the Principal Investigator at each study site. Protocols will be noted as approved by placement of the **Example** Representative's signature on the cover page. The Sponsor of the study will also approve the protocol by having a study-responsible individual sign the protocol cover page.

## 12.2.2 Informed Consent

An ICF that includes all of the relevant elements currently required by FDA and local state regulations will be provided to each prospective study subject at Screening, before enrollment into the study. In addition, subjects who are considered minors in the state the study is being conducted (< 18 years of age in most states) must have a signed parental/guardian ICF, indicating approval to participate, as well as a signed assent to participate form. The type and method of study, tests to be administered, any potential or possible hazards, and the subject's right to withdraw from the study at any time will be explained to the subjects by the Investigator or designee. Once the Investigator or designee is assured that an individual candidate understands the implications of participating in this study, the subject will be asked to give consent by signing and dating in the appropriate areas of the ICF or assent, as appropriate. The Investigator or designee will also sign and date the form, along with a staff member who will sign the ICF as a witness to verify that the subject has indeed received information. If any other language is required, translation will be performed by a certified translator. A copy of the ICF and/or assent will be provided to the subject.

## 12.2.3 Protocol and Informed Consent Changes

Sponsor approved changes to the protocol or the ICFs will be implemented as revisions to the original documents and will require additional review and approval by the IRB. Revisions to the original protocol will be documented in amendments, incorporated as a preface to the new version. Any revision that substantially alters the study design or increases potential risk to the subject requires the subject's consent to continue in the study. The approvals will be processed in

A Randomized, Multiple-Dose, Blinded, Placebo-Controlled, Parallel-Design, Multiple-Center, Clinical Study to Evaluate the Therapeutic Equivalence of Fluticasone Propionate and Salmeterol Inhalation Powder, 100 mcg/50 mcg (Supplied by Teva Pharmaceuticals Ireland) to ADVAIR DISKUS® 100/50 (fluticasone propionate/salmeterol) Inhalation Powder, (GlaxoSmithKline) in Subjects With Asthma

accordance with the established IRB procedures. Copies of all protocol and ICF amendments/revisions, along with letters noting IRB approval, will be submitted to the Sponsor.

## 12.2.4 Source Documents and Case Report Forms

All subjects will be identified by initials, date of birth, and a unique subject number. Source documents will be used to record all study-related data. Source document entries will be used to complete eCRFs. All data and eCRFs will be reviewed, evaluated, and signed by the Investigator, as required.

The original source documents and a copy of the corresponding eCRFs will be retained by the Investigator. Subjects who terminate early from the study will have the Visit 3 (end of study) source/eCRF completed.

## 12.2.5 Drug Accountability

All study product receipt, inventory, dispensing, dosing, and reconciliation records will be maintained in compliance with federal regulations. The study product will be dispensed to qualified study subjects according to established procedures. At the end of the study (i.e., at the site's close-out visit) all used and unused study product will be returned to Sponsor or designee.

## 12.2.6 Drug Storage

All study product will be stored at controlled room temperature between  $20^{\circ}$  and  $25^{\circ}$ C (68° and 77°F) with excursions permitted from  $15^{\circ}$  to  $30^{\circ}$ C (59° and 86°F), away from direct heat or sunlight in a secure, dry place with access by authorized individuals only. Any excursions from the permitted range of  $15-30^{\circ}$ C (59°-86°F) will require prompt notification to **15**, and thereafter **15** will notify the Sponsor Designee. The Investigator will be responsible for maintaining accurate records of drug receipt, dispensing, and return. At the end of the study, all partially used and unused study products will be returned to Sponsor or designee.

## 12.2.7 Retention of Reserve Samples

For every study product shipment received at the Investigator's site, the Investigator (or designee) will randomly select study product kits for retention. The selection process will ensure a sufficient amount of retention samples are retained as per Sponsor requirement. The number of each subject kit kept for retention will be noted on the drug accountability form as a retention sample, in addition to the retention sample log. These retention samples should be stored under the appropriate storage conditions for a minimum of 5 years following the application approval or, if not approved, at least 5 years after the completion of the study. Retention samples should not be returned to Sponsor/CRO/packaging group at any time. The retention samples will be shipped to a third party storage facility:

A Randomized, Multiple-Dose, Blinded, Placebo-Controlled, Parallel-Design, Multiple-Center, Clinical Study to Evaluate the Therapeutic Equivalence of Fluticasone Propionate and Salmeterol Inhalation Powder, 100 mcg/50 mcg (Supplied by Teva Pharmaceuticals Ireland) to ADVAIR DISKUS® 100/50 (fluticasone propionate/salmeterol) Inhalation Powder, (GlaxoSmithKline) in Subjects With Asthma

